#### 5.1.2. Secondary Endpoint

The change in pyridoxal 5'-phosphate (PLP) from Baseline to pre-3rd dose Week 9. Baseline is defined as the average of all available pre-dose assessments prior to first SC injection with asfotase alfa (-168, -156, -24, -12h, and pre-dose Day 1). Pre-3rd dose Week 9 is defined as the value obtained prior to the 3rd dose during Week 9.

### 5.2. Pharmacokinetic Endpoints

Pharmacokinetic endpoints and analysis will be discussed in a separate PK analysis plan.

#### 5.3. Safety

Safety endpoints will include: adverse events (AEs), vital signs, laboratory assessments, physical examination, renal ultrasound, and ophthalmology examination, urine pregnancy tests, and antibodies. Each is described in further detail below.

#### 5.3.1. Adverse Events (AEs)

Adverse events are defined in Protocol Section 9.4.1. This includes serious adverse events [SAEs], injection site reactions [ISRs], injection associated reactions [IARs], discontinuations due to AEs, drug-related serious and severe AEs. Also refer to Appendix 9.3 of this SAP for special handling of AEs.

Adverse events of special interest (AESI) include: ISR, Hypersensitivity (IAR), ectopic calcification, lipodystrophy, craniosynostosis, and chronic hepatitis. The AESI of ISR and hypersensitivity (IAR) will be identified by investigators as captured on case report forms. They will be supplemented by additional events identified by an Alexion clinical review and which are considered to be at least possibly related to study drug. The AESI of ectopic calcification, lipodystrophy, craniosynostosis, and chronic hepatitis will be identified by an Alexion clinical review irrespective of the event relationship to study drug.

#### 5.3.2. Vital Signs

The following vital signs will be recorded at the times specified in Appendix 9.1: systolic and diastolic blood pressure (millimeters of mercury [mmHg]), heart rate (beats/minute), respiratory rate (breaths/minute), and temperature (degrees Celsius [°C] or degrees Fahrenheit [°F]). On dosing days in the clinic or under medical supervision at home, vital signs will be taken within 10 minutes before study drug injection.

#### 5.3.3. Laboratory Assessments

Serum chemistry, hematology, and urinalysis testing will be performed at the times specified in Appendix 9.1. Specific laboratory assessments are provided in Appendix 14.1 of the protocol. Laboratory testing will also include Vitamin D, serum parathyroid hormone (PTH), and urine Ca:Creatinine at the times specified in Appendix 9.1. A central laboratory (Covance) will be used for laboratory testing and Clinical Significance (CS) will be assigned by the investigator.

In addition, a serum sample for tryptase will be collected pre-dose on Day 1 and analyzed if the patient experiences a subsequent Hypersensitivity (IAR). In the case of systemic hypersensitivity reactions, the investigational site will collect laboratory samples for analysis of the following: • Tryptase within 1 hour from time of reaction onset, if possible (no longer than 2 hours after

• Tryptase within 1 hour from time of reaction onset, if possible (no longer than 2 hours after onset) and at 24 hours (or later) from time of reaction onset

• C5b-9 within 24 hours from time of reaction onset

• Hematology, blood chemistry, and urinalysis within 3 hours from time of reaction onset and at 24 hours from time of reaction onset

Finally, HPP genetic testing will also be performed at entry into the study.

#### 5.3.4. Physical Examinations

At Screening and Baseline visits, a complete physical examination will be performed. Thereafter, limited physical examinations (based on the patient's signs/symptoms) may be performed at the times specified in Appendix 9.1 using a standardized form with a checklist of items: general appearance; skin; head; ear; eye; nose; throat; neck; lymph nodes; chest; heart; abdominal cavity; limbs; central nervous system; and musculoskeletal. All physical examinations (complete and limited) will include weight (using a calibrated scale) and examination of asfotase alfa injection sites for potential reaction(s). The Screening and Baseline physical examination will include height (using a wall-mounted standiometer).

#### 5.3.5. Renal Ultrasound

A renal ultrasound will be performed at the times specified in Appendix 9.1 to assess for the presence of nephrocalcinosis.

#### 5.3.6. Ophthalmology Assessment

A full ophthalmology examination will be performed at the times specified in Appendix 9.1. The examination will assess for papilledema and signs of ectopic calcification, and will include assessments of visual acuity; adnexa; and slit-lamp biomicroscopy with examination of anterior chamber, lens, conjunctiva, cornea, fundus, and other.

#### 5.3.7. Urine Pregnancy Test

Pregnancy data will be performed in all female patients of childbearing potential.

#### 5.3.8. Anti-Drug Antibodies (ADA) and Neutralizing Antibodies (NAb)

Patients will be monitored for development of antibody production against asfotase alfa (asfotase alfa ADA) throughout this study at the times specified in Appendix 9.1. Serum will be collected and analyzed for the presence of ADA, and if positive, further analyzed for titer and NAb.

The following definitions will be applied to categorize ADA and NAb post-baseline results:

- ADA positive status
  - Positive (Ever)

Patients who had at least 1 positive post-baseline value for ADA

- Negative (Always)

Patients who never had a positive post-baseline value for ADA

- ADA continuously positive status (evaluated in the exposure based analysis only)
  - Continuously Positive Criteria:

To be continuously positive a patient must have achieved, and sustained, uninterrupted positive results for ADA during and through the end of their series of post-baseline ADA measures. At a minimum, patients must be positive for the last 2 post-baseline measures of all time points when patients were tested for ADAs (e.g., being positive only at the last measure is not sufficient to confer continuously positive status).

Patients whose ADA Status was "Positive (Ever)" and had ADA values that met the Continuously Positive Criteria described above.

- Not Continuously Positive

Patients whose ADA Status was "Negative (Always)", or

Patients whose ADA Status was "Positive (Ever)" and had ADA values that did not met the Continuously Positive Criteria described above.

- ADA high and low titer status (evaluated in the exposure based analysis only)
  - High Titer

Patients whose ADA Status was "Positive (Ever)" and whose maximum postbaseline value for ADA was > 128.

- Low Titer

Patients whose ADA Status was "Positive (Ever)" and whose maximum postbaseline value for ADA was <= 128.

- NAb positive status
  - NAb Positive Criteria:

Neutralizing antibody subgroups will be determined using the NAb percent inhibition levels where < 4.478 will be considered "Negative" and >=4.478 will be considered "Positive".

NAb positive status may only be determined for observations that were concurrently positive for ADA. Accordingly, all observations where patients were negative for ADAs will automatically set the NAb status to negative and any analyses of NAb inhibition will also be omitted. – Positive (Ever)

Patients who had at least 1 positive post-baseline value for NAb

- Negative (Always)

Patients who never had a positive post-baseline value for NAb

# 6. DATA SETS ANALYZED (STUDY POPULATIONS)

# 6.1. Full Analysis (FA) Set

Patients who have been randomized and received at least one dose of study drug that have at least one pre-treatment and one on-treatment PPi result will be included in the FA set. Patients will be included in the analyses according to the treatment cohort to which they were randomized, irrespective of the treatment they actually received.

# 6.2. Per Protocol (PP) Set

Patients meeting the definition of FA Set (see above) and who are without major protocol deviations will be included in the PP Set. Major protocol deviations will include:

• Non-compliance with study treatment; compliance for a single dose will be defined as receiving the assigned cohort dose with a 10% window around expected mg administered.

• Not receiving all doses of study drug during Weeks 8 and 9 and at least 80% of study drug as specified in the protocol.

- Not receiving the correct study treatment
- Failing to meet key (pre-defined) eligibility criteria
- Other major protocol violations

Determination of whether or not a patient will be excluded from the PP Set will be made prior to the database lock.

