(3 times per	Week 4	Day 22: pre-dose, post-dose 6h	D22, D24, D26	All	Day 22: pre-dose
week)	Week 5	Day 29: pre-dose (trough), post-dose 6h	D29, D31, D33	All	Day 29: pre-dose
	Week 6	None	D36, D38, D40	None	None
	Week 7	Day 43: pre-dose (trough), post-dose 6h	D43, D45, D47	All	Day 43: pre-dose
	Week 8	Day 50: pre-dose (trough), post-dose 6h	D50, D52, D54	All	Day 50: pre-dose
	Week 9	Day 57: pre-dose Day 61: pre-dose (trough), post-dose 6h, 12h Day 62:post-D61 dose 24h, 32h, 36h, Day 63:post-D61 dose 48h, 56h, 60h	D57, D59, D61	All	Day 61: pre-dose
No Dosing	Week 10	Day 64: post-D61 dose 72h Day 65: post-D61 dose 96h Day 66: post-D61 dose 120h Day 67: post-D61 dose 144h Day 68: post-D61 dose 168h	None	All	Day 68: post-D61 dose 168h
	Week 11	Day 71: post-D61 dose 240h Day 75: post-D61 dose 336h	None	All	Day 75: post-D61 dose 336h
	Week 12	Day 80: post-D61 dose 456h	None	All	Day 80: post-D61 dose 456h
	Week 13	Day 87: post-D61 dose 624h	None	All	Day 87: post-D61 dose 624h

Abbreviations: ADA = anti-drug antibodies; PK = pharmacokinetics; PLP = pyridoxal 5'-phosphate; PPi = inorganic pyrophosphate; SOM = Study Operations Manual; D = day; h = hour

NOTE: Trough is defined as pre-dose concentration (ie, concentration data-point collected just prior to the next dose).

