## 11.5.4. Efficacy/Pharmacodynamic Analyses

## 11.5.4.1. Primary Efficacy/Pharmacodynamic Endpoint

The primary efficacy/PD endpoint will be the change from PPi Baseline to pre-3rd dose Week 9. Baseline is defined as the average of all available Run-in Period assessments on or prior to first SC injection with asfotase alfa. Pre-3rd dose Week 9 is defined as the value obtained prior to the third dose during Week 9. To assess differences between cohorts, the Wilcoxon rank-sum test will be used. A fixed sequence testing procedure will be performed with the comparison of the 9.0 mg/kg/week cohort compared to the 1.5 mg/kg/week cohort being performed first, and the hypothesis testing for the second comparison 6.0 mg/kg/week cohort compared to the 1.5 mg/kg/week cohort only being performed if the null hypothesis is rejected for the previous comparison at a significance level of 0.05. The primary endpoint will be met if the null hypothesis is rejected for both comparisons at a significance level of 0.05. Additionally, the shift in the distributions and 95% confidence interval (CI) for the above comparisons will be reported using the Hodges-Lehmann-Sen estimate and the exact confidence limits reported.

As secondary analyses, descriptive statistics for absolute PPi level and the change from Baseline will be summarized at all study timepoints by cohort. Within cohort, the change from Baseline to all study timepoints will be analyzed using the Wilcoxon signed-rank test.

Additionally, a restricted maximum likelihood (REML)-based repeated measures mixed model will be fit to estimate the change from Baseline in PPi at each pre-dose timepoint during the study period and test whether the change differs from zero at each timepoint. The analysis will include the fixed, categorical effect of visit. An unstructured covariance structure will be used to model the within-patient errors. If this analysis fails to converge, the following structures will be tested and the final covariance structure will be determined by Akaike's information criterion (AIC): first-order autoregressive, compound symmetry, and Toeplitz. The Kenward-Roger approximation will be used to estimate denominator degrees of freedom. The estimate of change from Baseline at defined visits will be provided, along with 95% CIs and p-values. The treatment effect will also be explored.

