# 4.1. Changes from Analyses Specified in the Protocol

The primary analysis of the primary endpoint, the change in PPi from Baseline to pre-3rd dose Week 9 has been changed from non-parametric exact Wilcoxon rank-sum test into a restricted maximum likelihood (REML)-based repeated measures mixed model; while non-parametric exact Wilcoxon rank-sum test becomes a supportive analysis.

The Per Protocol Set criteria for study drug compliance has been modified as 100% compliance (i.e. all doses of study drug) is too restrictive. A slightly revised definition will be utilized requiring that patients receive 100% of study drug as planned on Weeks 8 and 9, and at least 80% of study drug overall as specified in the protocol.

All prior and concomitant medications and therapies must be collected from 30 days prior to study entry up until the final study visit. The protocol has inconsistent description of the process for the collection of Concomitant medications and therapies in Table 2, footnote 9 and Section 8.7; this is being clarified with an administrative letter.

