#### 7.2.1. Primary Endpoint

The primary endpoint for this study is the change in PPi from Baseline to pre-3rd dose Week 9. Change from Baseline in PPi will be the primary variable. Primary analysis will be performed by using a restricted maximum likelihood (REML)-based repeated measures mixed model, fit for each treatment cohort to estimate the change at each pre-dose (trough) timepoint starting at Week 4 (Day 22) through Week 9 (Day 61). The primary hypotheses will test whether the differences between the cohorts differ from zero at pre-3rd dose Week 9. The Week 3 (Day 15) pre-dose timepoint will not be included in the model assessing change since this is expected to be similar to a baseline level of PPi after the first non-dosing period. The analysis will include the fixed, categorical effect of visit, adjusted for baseline PPi, gender, baseline weight group ( $\geq$  median versus < median), and study drug lot assignment. An unstructured covariance structure will be used to model the within-patient errors. If this analysis fails to converge, the following structures will be tested and the final covariance structure will be determined by Akaike's information criterion (AIC): first-order autoregressive, compound symmetry, and Toeplitz. The Kenward-

Roger approximation will be used to estimate denominator degrees of freedom. The estimated mean change from Baseline at each visit from the model will be provided, along with 95% CIs and p-values.

A fixed sequence testing procedure will be performed with the comparison of the 3.0 mg/kg cohort compared with the 0.5 mg/kg cohort being performed first, and the hypothesis testing for the second comparison 2.0 mg/kg cohort compared with the 0.5 mg/kg cohort only being performed if the null hypothesis is rejected for the previous comparison at a significance level of 0.05 (p-value <0.05). The primary endpoint will be met if the null hypothesis is rejected for both comparisons at a significance level of 0.05 (both p-values <0.05).

The same model will additionally be employed with the fixed, categorical effect of visit, adjusted for baseline PPi.

A similar modeling approach will be employed to explore the effect of treatment cohort on the change from Baseline in PPi at each pre-dose timepoint.

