As supportive analysis, the non-parametric exact Wilcoxon rank-sum test will be used to assess differences between treatment cohorts, using both last observation carried forward (LOCF) and observed case (OC) methods. The location shift in the change from Baseline distributions and 95% CI for the above comparisons will be reported using the Hodges-Lehmann-Sen estimate and the exact confidence limits reported.

To examine the change from Baseline in PPi, descriptive statistics for the absolute PPi level and the change from Baseline will be summarized at all study timepoints by treatment cohort, spanning from Week 1 to Week 13; Baseline will be calculated in the same way as for the primary analysis. Within cohort, the change from Baseline to all study timepoints will be analyzed using the non-parametric Wilcoxon signed-rank test.

Individual and mean PPi levels for each cohort versus time curves will be presented with normal references ranges indicated (see Appendix 9.3). Please refer to Table 4 on how to handle the values fall under the lower limit of quantification (LLOQ). Additional analysis of PPi data may be performed if considered useful.

The above analyses for PPi will additionally be performed using the PP Set.

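### The Per Protocol Set requires the Day 61 dose, which follows the sample defining the PPi and PLP endpoints, so a missed Day 61 dose excludes patients with a valid endpoint

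*SAP*

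**What the plan says.** SAP 6.2 defines the PP Set as Full Analysis (FA) Set patients without major protocol deviations. The dosing deviation is "Not receiving all doses of study drug during Weeks 8 and 9", coupled in the same bullet with an 80% minimum. SAP 4.1 presents this as a relaxation of the protocol's all-doses rule, which it calls too restrictive, and describes it as "requiring that patients receive 100% of study drug as planned on Weeks 8 and 9" together with at least 80% overall. The first bullet of SAP 6.2 adds a dose-level condition: a single dose is compliant if it lies within 10% of the expected milligrams. No exception is made for Day 61.

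Protocol 11.5.4.1 says the pre-3rd-dose Week 9 value is "defined as the value obtained prior to the third dose during Week 9". SAP 5.1.1 and 5.1.2 use the same timepoint for PPi and PLP. Protocol Table 3 gives the Week 9 doses as Days 57, 59 and 61, and orders the sampling as "Day 61: pre-dose (trough), post-dose 6h, 12h". The repeated measures model in SAP 7.2.1 ends at the Day 61 trough.

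SAP 7.2.1 closes with "The above analyses for PPi will additionally be performed using the PP Set", and SAP 7.2.2 applies similar methods to PLP in both sets. Protocol 11.1.2 calls the PP efficacy analyses secondary.

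**The concern.** Full dosing in the last two weeks is a sensible PP requirement if the aim is to secure exposure leading into the endpoint. The Day 61 dose adds nothing to that aim, because the endpoint sample has already been drawn. Two patients with identical dosing and identical data up to the endpoint are classified differently because of what happened afterwards.

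For the endpoint analyses, the condition discards usable data from small cohorts. It could also select patients. The study is open-label (Protocol 8.6), and after a moderate or severe injection-associated reaction the investigator decides with the medical monitor whether injections continue (Protocol 9.4.2.1.1). If a withheld Day 61 dose were related to cohort, exclusions would be too. The documents give no rate, so this is only a possibility.

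**Working it through.** **The plan's own figure.** The sample-size statement (Protocol 11.5.8, SAP 9.2) is used below as a yardstick. It assumes SD 1.5 µM and a two-sided two-sample t-test at 0.05. Power comes from the noncentral t with noncentrality d / [SD × √(1/n1 + 1/n2)].
- 9 v 9, d = 2.3: 2.3 / (1.5 × √(2/9)) = 3.25 on 16 df, power 86.3%. The plan says above 80%.
- 6 v 6, d = 3.2: 3.2 / (1.5 × √(2/6)) = 3.70 on 10 df, power 91.4%. The plan says above 90%.

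Both reproduce for a single comparison and are not in dispute.

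**Dose count (Protocol Table 3).**
- Scheduled doses: 1 single dose + 7 weeks × 3 = 22.
- Due before the Day 61 sample: 21. Due after it: 1 (Day 61).
- Weeks 8 and 9: Days 50, 52, 54, 57, 59 and 61, so 6 doses, 5 of them before the sample.

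**The rule applied to a patient who lacks only Day 61.**
- Dosing up to the endpoint: 21/21 = 100%.
- Dosing overall: 21/22 = 95.5%, which passes the 80% requirement.
- Weeks 8 and 9: 5 of 6, which fails. The patient leaves the PP Set.

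**The 80% requirement.** 0.8 × 22 = 17.6, so 18 of 22 doses are needed. Counted before the sample, 0.8 × 21 = 16.8, so 17 of 21. The two differ only for a patient with exactly 17 earlier doses and no Day 61 dose.

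**PP outputs on each side of the Day 61 dose.**
- Before it: change to pre-3rd dose Week 9 in PPi and PLP, and the repeated measures model through the Day 61 trough.
- After it: summaries, signed-rank tests and curves running to Week 13. Table 3 times 17 samples from the Day 61 dose: 8 from 6h to 60h, 5 from 72h to 168h, then 240h, 336h, 456h and 624h.

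**Size of losing patients, assuming 9 per cohort beforehand.**
- SE of one cohort mean, 9 to 8 patients: √(9/8) = 1.06.
- SE of a two-cohort contrast, one patient lost: √[(1/8 + 1/9) / (2/9)] = 1.03.

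| Patients compared | Noncentrality (d = 2.3) | t-test power |
|---|---|---|
| 9 v 9 | 3.25 | 86.3% |
| 9 v 8 | 3.16 | 83.9% |
| 8 v 8 | 3.07 | 81.4% |
| 9 v 7 | 3.04 | 80.8% |

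These are t-test figures on the planning assumptions. They show relative cost and are not the power of the SAP's mixed model.

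**The case against.** The strongest objection is that the PP Set does not serve the Week 9 endpoint alone. The same set is used for PPi outputs to Week 13, and a patient not dosed on Day 61 has no valid values timed from that dose. There the Day 61 condition is relevant, and deleting it from the single PP definition would let such patients into those outputs. This stands. A reader might infer that the condition is pointless throughout and can simply be struck out. SAP 7.2.1 does not support that.

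Second, the case is probably uncommon. Day 61 falls in a required in-clinic week with dosing at the site (Protocol Table 2, footnotes 12 and 14; Protocol 8.5). The scenario needs a patient who attends, gives the trough sample and is then not dosed. If the whole visit is missed, the sample is missing too and no valid endpoint is discarded. This also stands.

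Third, a reader might infer that a Day 61 dose outside the 10% window excludes a patient automatically. The first bullet defines compliance for one dose but does not say how many non-compliant doses make a patient non-compliant. Such a dose may have this effect, but the text does not settle it.

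Fourth, exclusion on post-randomisation events is inherent in any PP set. That is true, but such exclusions are normally justified by their bearing on the endpoint, and this one has none.

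**Conclusion.** The point holds as a minor improvement. As written, SAP 6.2 and 4.1 exclude from the PP analyses of the PPi and PLP endpoints a patient who was fully dosed up to the endpoint sample and lacks only the later Day 61 dose. This follows from the dosing and sampling schedule and needs no assumption about the data.

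The consequence is limited. On the planning assumptions with about 9 per cohort, one lost patient costs 3% in the standard error of a contrast and about 2 points of t-test power (86.3% to 83.9%). The number of such patients is unknown and probably small.

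A reader might go further and conclude that the primary result is at risk or that the PP results are biased between cohorts. The documents support neither. The primary analysis is on the FA Set, which keeps these patients, and nothing shows that Day 61 doses would be missed more often in one cohort than another.

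**What to change.** Before database lock, amend SAP 6.2 and 4.1 as follows:

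- **Week 9 endpoint analyses.** For PP analyses of change to pre-3rd dose Week 9 in PPi and PLP, including the repeated measures model through the Day 61 trough, apply the all-doses, 10% window and 80% criteria only to doses due before the Day 61 pre-dose sample, that is, through Day 59. All three criteria need the change. Editing the Weeks 8 and 9 phrase alone would leave the 10% window applying to Day 61.
- **Later timepoints.** Keep the Day 61 condition for PP summaries, tests and curves after the Day 61 dose.
- **Sensitivity analysis.** Align in the same way the optional analysis in SAP 7.2.1.5 that is restricted to patients with complete dosing through Week 9.
- **Endpoint sample.** State that the scheduled Day 61 trough remains the endpoint sample if the dose is then not given.

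The cost is a short wording change and one additional population flag. The PP population may differ slightly between the Week 9 endpoint outputs and the later ones, so table footnotes should say which flag applies. Dosing, data collection and the primary analysis do not change.
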